## **CONSENT PROCESS**

We have received waivers of consent for clinic randomization and for patients surveyed as part of Aim 3.

We have received a waiver of documentation of consent for providers and clinic staff surveyed and interviewed as a part of Aim 3.

### Electronic presentation of consent information

For Aims 3 and 4, participants completing surveys and interviews will be directed to a REDCap survey. The first page of the survey will have a brief overview of the study and will include contact information for the study staff. The recruitment email for Aim 4 contains consent information as well.

For Aim 1, although consent is being waived so as to reduce bias, patients completing the risk assessment questionnaire will be presented with a brief description of the study and the type of information the risk assessment questionnaire will collect, as well as contact information for the study staff. Patients will be given the option to either start the survey or skip the survey and answer some brief questions as to why they do not want to complete the survey.

## **PRIVACY AND CONFIDENTIALITY**

### **Privacy protections**

Outreach materials will clearly identify the clinic that provided the individual's contact information and emphasize that this a general mailing simply based on them having been seen at a clinic participating in the study. No personal medical information was used to determine if they receive a mailing or not and they are free to opt out of any additional outreach. The consent information for those being interviewed will state that audio recordings of interviews will be transcribed in a manner that removes identifying information and the recordings and transcripts will be destroyed after the records retention period required by state and federal law.

Previvors should not have any privacy concerns. We will state how we have obtained their information in recruitment and all assessments will be administered through REDCap. The consent information for those being interviewed will state that audio recordings of interviews will be transcribed in a manner that removes identifying information and the recordings and transcripts will be destroyed after the records retention period required by state and federal law.

## **RISK / BENEFIT ASSESSMENT**

### **Anticipated risks**

Risks include possible loss of confidentiality and psychological distress when understanding one's personal risk of developing cancer. In other studies, we have seen minimal negative reaction to testing information. However, we will monitor this process and measure any harm that might come to patients as a result of participation in this study.

The risk for the previvors is primarily distress (knowing they have a mutation in a gene associated with cancer). . In other studies, we have seen minimal negative reaction to testing information. Our assessment also try to ascertain this information as well. Previvors cannot be discriminated against due to their mutation status by employers or insurers as they are protected by federal law (Genetic Information Nondiscrimination Act)

We do not anticipate any risk to providers/clinic staff in any of our aims. At minimum, we ask providers and staff to reflect on their workplace and this may bring about negative feelings. The Aim 4 surveys are anonymous to clinic-level research staff (but not UW research staff) so there is no risk to employability or reputation.

### **Data and Safety Monitoring**

We will invite a Data Safety Monitoring Board to review our procedures and data, helping to ensure safety and confidence in the study procedures by participants and scholars. The DSMB will be composed of at least three people, a medical expert, a genetic counselor, and an advocate. They will review the study protocol, the procedures for recruitment and assessment, and the intervention documents to insure adherence to equity and to other ethical principles. They will review data at least annually to note any unanticipated negative effects, and will work with the PIs and investigators to consider changes in the procedures if necessary.

### **Anticipated direct benefits to participants**

Patients found to be at high risk will have access to genetic testing and genetic counseling. The study will cover the cost of these activities.

### **Return of individual research results**

Patients who complete the risk assessment questionnaire will have more information about their potential cancer risk. Those at high risk, for example, may benefit from more frequent screening and would meet the clinical guidelines for genetic testing. Patients that go on to have genetic testing will receive results that may lead a provider to recommend surgery or other interventions to reduce the risk of developing cancer.

Patients who complete the risk assessment questionnaire with a result that is not high risk will receive that information in the same way as patients with a high risk result. The result will be returned to the patient with the caveat that although they are not at high risk based on their family history, there may be environmental and behavioral factors that increase their potential risk of developing cancer. Patients who complete genetic testing with no mutations identified will receive a results report indicating this and explaining that there are other factors that can influence cancer risk, as well as the possibility of genetic links that are not yet known.

Note: the study is helping facilitate genetic testing, but the testing is not a research procedure.

Patients who complete the risk assessment questionnaire will receive their results online after answering the last question. Patients with a high risk result will be asked to provide their email address so that the study staff may contact them about proceeding with genetic testing. Patients who are not at high risk will have the option of providing their email address to receive a brief email with some online resources containing more information about cancer risk in general. Patients who complete the genetic testing will receive their results through the Color website three to four weeks after submitting their sample. The testing process involves setting up an online account and the patient will be able to choose whether or not they want to view their results. The results report explains the findings and provides information about how to interpret and use the results. Patients are also given the contact information to speak with a genetic counselor who can further explain the results and possible next steps.

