#### **Aim 3**

A random sample of active patients will be selected from each clinic and asked to complete a baseline survey. This sample will come out of the list of patients who meet the eligibility criteria defined in section 2.2. The clinic or a healthcare system representative will pull the contact information for the selected patients from their electronic medical record (EMR). The study staff will reach out using mail and email. Outreach materials will clearly state the role of the clinic in the study and as the source of the patient's contact information (see attached Study Recruitment Templates). This process will be repeated approximately 12 months later, to obtain a second snapshot of the patient population.

We are also interested in interviewing patients who have reached various stages in the risk assessment and genetic testing process. The patient names and contact information will be obtained by clinic staff or directly from the patient through the risk assessment survey.

For previvors (patients who test positive for one or more mutations) we receive the results from Color Genomics from patients who have agreed to allow Color to share their results and we implement the previvor assessment and intervention procedures, using email and telephone.

Providers, clinic staff, and clinic leaders at each clinic will be identified by a representative at the clinic. All of these individuals will be contacted. Contact information will come from the clinic's employee directory or a similar source. Outreach will be conducted using mail and email and will clearly state the role of the clinic in the study and as the source of the individual's contact information (see attached Study Recruitment Templates). A random sample of those who agree to be interviewed will be contacted for an interview.

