#### **Recruitment Materials**

Individuals invited to participate in the surveys and interviews will receive a letter and/or email introducing the study.

Patients visiting clinics in the POC arm will be given a tablet with the risk assessment website loaded (in-person visits), or walked through the risk assessment over the phone by a clinic staff member. A document with examples of talking points has been uploaded into Zipline. Patients in the POC arm may be approached by clinic staff that they are familiar with from previous visits to the clinic.

Patients in the DPE arm will receive a letter and email (for those who have an email address) introducing the study and providing a link to the study website.

Previvors will receive a phone call from study staff to explain the purpose of the previvor assessment. In this call, study staff will explain the purpose of the call, their role, and a brief overview of the assessment and an invitation to complete an interview in conjunction with the assessment. Study staff will empathize the patient's participation in the assessments and interviews is voluntary. The recruitment email, if patient is not contactable by phone, will have similar language. Both forms of outreach will give the study and a local clinic contact's contact information for patient's reference. If patient wishes to proceed, they will be sent a link to the REDCap survey to fill out the assessment and informed a study staff member will follow up to schedule an interview when they have had a chance to complete the assessment.

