### Testing

Patients who complete the risk assessment questionnaire and are found to be high risk should be offered genetic testing. This recommendation is part of standard clinical guidelines. Patients in the POC arm will be sent an email with more information and will be connected to the Color Genomics website to complete genetic testing, if desired.

Patients in the DPE arm will be sent from the risk assessment questionnaire directly to a site with more information and connected to the Color Genomics website to complete genetic testing, if desired. For the genetic testing, a testing kit will be mailed to the patient. Three to four weeks later, results will be sent to the patient and their provider.

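### Patients may choose not to view their genetic result, but previvor research contact is not conditioned on the patient already knowing it

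*Combined protocol and SAP*

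**What the plan says.** Under Return of individual research results, patients get their genetic result through an account on the laboratory's website, and "the patient will be able to choose whether or not they want to view their results".

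The Aim 3 part of Recruitment and Screening defines the group to be followed as "previvors (patients who test positive for one or more mutations"), with nothing about whether the patient has seen the result. It states the condition for release to the study: "we receive the results from Color Genomics from patients who have agreed to allow Color to share their results". It then says that "we implement the previvor assessment and intervention procedures, using email and telephone".

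Recruitment Materials describes the first contact: "Previvors will receive a phone call from study staff to explain the purpose of the previvor assessment". It adds a fallback: "The recruitment email, if patient is not contactable by phone, will have similar language". Privacy protections says of the same contact: "We will state how we have obtained their information in recruitment".

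Previvor Activities gives two timings. The survey assessment takes place at baseline, described as the time of first receipt of results, and again 6 months later. The same section also has every patient who tests positive interviewed ahead of receiving results and 6 months after. It does not define receipt.

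**The concern.** A patient who agrees that the laboratory may share a result with the study has not thereby asked to be told it. The plan offers a choice about viewing, then sets up a contact that goes only to people with a positive result and does not make it depend on that choice having been exercised.

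Two things are at stake. The first is participant protection. Under Anticipated risks, the plan names distress from knowledge of the mutation as the main risk to previvors. A research call or email could be how an unviewed positive result reaches the patient.

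The second is measurement. Aim 3 evaluates benefits and harms, and the previvor follow-up is meant to detect harm from testing. If some patients do not yet know their result when baseline distress is recorded, that value is not a reaction to the result. The 6-month interval then also lacks a common starting point.

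**Working it through.** The plan states no figure on this point, so the check sets the sections side by side.

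1. **Can a tested patient be unaware of a positive result?** Yes. Return of individual research results makes viewing optional.
2. **Can the study hold that patient's result?** Yes. Aim 3 recruitment requires only agreement to sharing, which is a separate decision from viewing.
3. **Does holding a positive result lead to contact?** Yes. Aim 3 recruitment and Recruitment Materials provide for a call, or an email if the call fails. Neither includes a step to establish whether the patient has viewed the result or wants to know it.
4. **Does the contact reveal the result?** It can. Only positives are contacted as previvors. Staff explain what the previvor assessment is for and, under Privacy protections, how the study obtained the patient's information. Together these let the patient work out the result. The sample questions under Data Collection go further and speak of a positive finding as something the patient already has.
5. **Does another section supply a check?** None does.
   - *Voluntariness.* Recruitment Materials says that participation is voluntary, but the patient hears this during the call.
   - *Consent.* The study overview stands on the first page of the REDCap survey, and for previvors the link to it is sent after the call. The Consent Process section reports a waiver for patients surveyed in Aim 3.
   - *Timing.* The receipt wording in Previvor Activities governs the assessment, not the recruitment call. It does not mention viewing, and the same section also places an interview before receipt.
   - *Monitoring.* The monitoring board reviews recruitment and assessment procedures and looks at data each year or more often, but no check of this kind is named.
6. **What follows for the data?** If receipt means that the report became available, baseline and 6-month times can precede the patient's knowledge. If it means that the report was opened, they cannot, but no step described in the plan tells the study when that happened. Under either meaning, the interview placed before receipt does not fit a baseline that measures reaction to the result.

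**The case against.** The strongest reply is that a timing rule already exists. Results are received through the website, where the patient decides whether to look, so receipt can fairly be read as opening the report. On that reading the assessment would come after viewing. This reading is open. It does not reach the recruitment call, however, and the interview scheduled before receipt in the same section undercuts it. Defining receipt would settle much of the point but not all of it.

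The recruitment templates, the previvor measures document and the laboratory's sharing terms are also separate documents that are not included here, and any of them may contain a check. That stands: the point is only that this protocol states none.

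A reader might also infer stronger things that the documents do not support:

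- *That the study overrides a recorded refusal.* The plan describes an option in an online account, and nobody is identified who agreed to sharing but declined to view. Recruitment Materials does not say that staff announce a result.
- *That the 6-month point is counted from release of the report.* No section says so; the starting point is simply undefined.
- *That the Testing section contradicts the choice.* It says "results will be sent to the patient and their provider", which is compatible with a report in an account that stays unopened. The protocol also labels that section as clinical context, not research procedure.
- *That a number of affected patients can be given.* The figure of about 200 under Number of Subjects is expected previvor participants, not all positives. Any non-viewing rate applied to it would be pure assumption.

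**Conclusion.** The concern holds as a gap between a stated patient choice and a stated contact rule. Followed as written, the plan allows a research call or email to reveal a positive result to a patient who has not viewed it, and allows baseline distress to be recorded before the patient knows. This is a possibility that the text leaves open, not a prediction that it will happen.

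The size is unknown, because the documents give no rate of non-viewing or late viewing. The conclusion assumes that agreement to sharing is separate from viewing, and that no unseen script or laboratory term already closes the gap. The primary outcomes, screening and testing uptake, are not affected. The point bears on participant protection and on the previvor harm data in Aim 3. It should be corrected before previvor contact begins.

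**What to change.** Reconcile the Aim 3 recruitment section, Recruitment Materials, Previvor Activities and Return of individual research results, as follows:

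- Make no research recruitment contact for the previvor assessment or interview until the study has a record that the patient already knows the result.
- Define receipt of results in Previvor Activities accordingly, and resolve the interview that it places before receipt.
- Date the baseline and 6-month research assessments from that point.
- Report, by arm, the number of positives not contacted for this reason.

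This concerns research contact only. The plan bundles the previvor assessment with an intervention and a report on next steps. How results and any such support reach patients clinically, including those who have not viewed a positive result, is for the sponsor to settle.

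The cost is revised protocol and call wording plus a viewed-status or confirmation field. The documents do not show that the laboratory supplies viewed status, so the field may have to be obtained another way. Some positives will enter research follow-up later or not at all, and the count by arm makes that loss visible. If a check already exists in another study document, a sentence in the protocol pointing to it would close the contact gap; receipt would still need its definition.

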## **STATISTICAL ANALYSIS PLAN**

The primary outcomes are the fraction of the clinic population that participates in the risk assessment screening and the fraction of the clinic population that undergoes genetic testing. We will look at how well the interventions did in terms of getting people to be screened and tested, and how it varies across clinics within treatment arms.

The outcomes are binary, i.e., whether or not each individual in the clinic population completed screening or genetic testing, and individuals are clustered within clinics. Only a minimal amount of identifying data will be required for the screening (ex: age, sex), therefore we plan to analyze two sets of data. The first includes data collected in aggregate at the clinic site level and the second includes data collected at the patient level and integrated additional data at the site level. Analyses of the primary outcomes will use the clinic as the unit of analysis, with the outcome variable for each clinic being the percent of that clinic's population who complete the screening assessment. We will perform a series of bivariate logistic regression models with scale adjustment for overdispersion. We will also use multivariable logistic regression to estimate and test the relative odds between the study arms for the primary outcomes.

We will estimate the value (cost effectiveness) of one screening strategy over the other, using the incremental cost effectiveness ratio (ICER) to determine which strategy provides more value for the investment made. We will express each of these outcomes as the cost per patient screened and the cost per patient tested.

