## OVERVIEW

### **Objectives**

The purpose of this study is to determine how to best implement appropriate genetic testing and follow-up care in the primary care setting.

**Aim 1:** Compare two strategies for identifying members of a primary care clinic's population who have a family or personal history of cancer and encouraging these high-risk individuals to obtain genetic testing for cancer susceptibility mutations. The two methods are: 1) Point of Care (POC) approach, completed in conjunction with a regularly scheduled appointment; and 2) Direct Patient Engagement (DPE), using letters and emails. Individuals will be asked to visit a web site for screening for family/personal history of cancer. Genetic testing will be recommended for those determined to be high risk. Outcomes will be the fraction of the clinic population that participates in the family/personal screening and the fraction of the clinic population that undergoes genetic testing.

Hypothesis 1: DPE screening will result in a higher proportion of active patients who screen for familial cancer risk compared with POC screening.

Hypothesis 2: Of screened patients, POC patients will produce a higher proportion of tested patients compared with DPE.

**Aim 2:** Identify changes, problems, and inefficiencies in clinical flow and interactions during and after the implementation of genetic testing.

**Aim 3:** Evaluate the effects of the two methods of implementation on patient, provider, and health system leader reports of benefits and harms, satisfaction, and perceived quality of care.

**Aim 4:** Evaluate the value (cost-effectiveness) and affordability (budget impact) of each method.

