#### Number of Subjects

As the clinics participating in the study have not yet been selected and we do not yet know how many patients would be considered “active” at each clinic, we are not able to estimate the total number of individuals who will be in the study.

We will recruit a total of 12 clinics.

We plan to consent approximately 6,000 patients (to complete surveys and interviews).

We plan to consent approximately 250 providers, clinic staff, and clinic leaders.

We estimate that approximately 200,000 patients will have the opportunity to complete the risk assessment questionnaire and around 3,000 will complete the genetic testing.

Of the patients who complete genetic testing, we anticipate that approximately 200 will participate in a previvor assessment and intervention (described below) because they test positive for one or more mutations.

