#### ***Aim 1***

To compare two strategies to identify and test high-risk individuals within primary care clinics, the 12 clinics will be randomized such that half will use the first method and half will use the second.

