### Randomization of clinics

Once the baseline assessment is complete, randomization will occur at the level of the clinic (within healthcare system). We will block on healthcare system and clinic size to help ensure comparable arms.

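### The ICER is the only stated basis for judging value, with no uncertainty method or rule for a near-zero or negative difference; cost per patient tested may be unstable with six clinics per arm

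*Combined protocol and SAP*

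**What the plan says.** The last paragraph of the Statistical Analysis Plan covers cost-effectiveness in two sentences. The strategies are to be compared "using the incremental cost effectiveness ratio (ICER) to determine which strategy provides more value for the investment made", and then: "We will express each of these outcomes as the cost per patient screened and the cost per patient tested." Aim 4 in the Objectives section adds only that value and budget impact will be evaluated.

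Nothing is said about an interval for the ratio, a willingness-to-pay value, dominance, a difference that is negative or close to zero, or two ratios that favour different strategies.

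Three other places bear on this:

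- Objectives, Hypotheses 1 and 2. The first expects direct patient engagement (DPE) to screen the larger share of active patients. The second reverses the direction at the next step: "Of screened patients, POC patients will produce a higher proportion of tested patients compared with DPE." Neither gives a size.
- Aim 1 under Recruitment and Screening: "the 12 clinics will be randomized such that half will use the first method and half will use the second."
- Randomization of clinics: "We will block on healthcare system and clinic size to help ensure comparable arms."

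**The concern.** A ratio of incremental cost to incremental effect loses information when the effect difference can take either sign. A negative ICER describes both a strategy that is cheaper and achieves more and one that is dearer and achieves less. A positive ICER describes both paying more for more and saving money by achieving less. As the effect difference approaches zero, the ratio grows without limit and changes sign on crossing it. The ratio alone therefore cannot do what the plan asks of it, which is to say which strategy gives more value.

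This matters here because the study's own hypotheses pull the fraction tested in opposite directions. If both are right, the denominator of cost per patient tested shrinks, and with few clinics its estimate is imprecise. Aim 4 could then name a preferred strategy on the strength of noise, with no stated uncertainty to warn the reader.

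**Working it through.** The documents give no arm difference, intraclass correlation, between-clinic variation or cost, so there is no planned figure to reproduce. The check asks how far the denominator could be from stable under stated assumptions.

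**Step 1: can the denominator be small?** Fraction tested = (fraction screened) × (fraction tested among screened). So the DPE/POC ratio for testing is the DPE/POC screening ratio divided by the POC/DPE ratio of testing among those screened:

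- 1.5 / 1.5 = 1.0, a difference of exactly zero
- 1.5 / 1.25 = 1.2
- 2 / 1.0 = 2.0

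Both hypotheses can be true while the net difference is nil, modest or large.

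**Step 2: inputs for the illustration.** From Number of Subjects: "We will recruit a total of 12 clinics", so 6 per arm, and "approximately 200,000 patients will have the opportunity to complete the risk assessment questionnaire and around 3,000 will complete the genetic testing". The pooled level is 3,000 / 200,000 = 1.5%, and equal clinics would have 200,000 / 12 = 16,667 patients. Assumed: a between-clinic coefficient of variation (CV) of 0.10, 0.25 or 0.5, the same in both arms; equal clinic sizes; no gain from blocking; arm ratios of 1.25, 1.5 or 2 around a mean of 1.5%.

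**Step 3: standard error of the arm difference.**

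SE = √{[(CV·p1)² + (CV·p2)²]/6 + [p1(1−p1) + p2(1−p2)]/(6 × 16,667)}

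Worked case, CV 0.25 and ratio 1.25: p1 = 1.333%, p2 = 1.667%, difference 0.333 points. In squared percentage points, the between-clinic term is (0.3333² + 0.4167²)/6 = 0.0475 and the patient-level term is 0.0030. SE = √0.0504 = 0.2245 points. Clinic variation dominates; patient-level error alone would give only 0.054 points.

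**Step 4: two probabilities.**

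- Wrong sign: Φ(−difference/SE) = Φ(−0.333/0.2245) = Φ(−1.485) = 7%.
- Unbounded interval: a 95% Fieller interval for the ratio is unbounded when the 95% interval for the denominator includes zero. That is the probability that |T| < 2.228, with T noncentral t on 10 degrees of freedom and noncentrality 1.485, which is 73%.

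The same steps give (wrong sign / unbounded interval):

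| CV | ratio 1.25 | ratio 1.5 | ratio 2 |
|---|---|---|---|
| 0.10 | 0.1% / 17% | <0.1% / 0.1% | smaller still |
| 0.25 | 7% / 73% | 0.4% / 34% | <0.1% / 3% |
| 0.5 | 22% / 89% | 9% / 77% | 1.5% / 50% |

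**Step 5: does the 1.5% level matter?** Hardly. With CV 0.5 and ratio 1.5, assumed levels of 5%, 10% and 20% each give about 9% / 77%, as at 1.5%. The level nearly cancels. What counts is the relative difference, the CV and the number of clinics.

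**The case against.** The strongest reply is that no instability is shown, because the documents contain none of the quantities that would show it. A reader might infer from the small share tested and the 12 clinics that the denominator is probably close to zero. That inference fails. The 1.5% is a level pooled over both arms, not a difference between them, and Step 5 shows that it has almost no influence. Nor do the hypotheses make cancellation probable: they give directions only, and a large screening effect with similar testing rates among those screened leaves a clear net difference. This part of the objection stands, and the claim is limited to what may happen.

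A reader might also infer that the planned odds-ratio models leave the team without an arm difference to put in the denominator. They do not: the plan makes each clinic's percentage the outcome, and the difference follows directly from those. What is missing is a stated interval for it.

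Three further points have some force.

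- Computing an ICER requires the incremental cost and effect, whose signs would reveal dominance, and the plan does not say they will be withheld. But it does not say they will be reported or used either.
- The sentence on cost per patient screened and tested could mean average costs within each arm, which have no difference in the denominator. The sentence before it still names the incremental ratio as the deciding quantity.
- Blocking on health system and clinic size could improve precision and is ignored above. Unequal clinic sizes would tend to work the other way.

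Finally, net benefit does not cure the imprecision of 12 clinics. That is true; it only expresses it in a quantity that stays finite and keeps one meaning.

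**Conclusion.** The concern holds in a limited form. The plan gives the ICER a deciding role without an uncertainty method or a rule for a negative or near-zero difference. That gap exists whatever numbers are assumed. For cost per patient tested, the opposing hypotheses and six clinics per arm make an unstable or uninterpretable ratio a realistic possibility.

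Its size is not determined by the documents. Over the assumed CVs of 0.10 to 0.5 and arm ratios of 1.25 to 2, it runs from almost no risk to a 22% chance of the wrong sign and an 89% chance of an unbounded interval. If the two hypothesised effects cancelled exactly, either sign would be equally likely.

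For cost per patient screened the concern is weaker: Hypothesis 1 expects a difference and no opposing effect is hypothesised, although no size is given. A reading that condemns both ratios equally goes too far. The point affects the Aim 4 conclusion, not the primary outcomes, and should be settled before the data are analysed.

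**What to change.** Amend the cost-effectiveness paragraph of the Statistical Analysis Plan so that the ICER alone is not the deciding quantity.

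1. Report separately the incremental cost per active patient, the arm difference in the fraction screened and the arm difference in the fraction tested. Give each a clinic-level interval from the 12 clinic values, t-based or by resampling clinics, accounting for the blocking factors. This step needs no figure from outside the study.
2. Base the value comparison on incremental net benefit. For each clinic compute (willingness to pay × fraction tested) − cost per active patient, and compare the arms with the same clinic-level intervals over a stated range of willingness to pay per additional patient tested. Repeat for screening, with its own range per additional patient screened.
3. Give the ICER as a descriptive point estimate, and state dominance where one strategy costs less and achieves more.

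The cost is a few sentences of SAP wording and a small additional analysis. The real downside is that a willingness-to-pay range must be chosen and justified, since the documents offer none.
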